7. STUDY OBJECTIVES

7.1 Primary Objective

The primary objective of this study is to evaluate the clinical benefit of the long variant of the CHIMAERA™ used in adult patients according to the manufacturer IFU in routine clinical practice from the time of surgery within 12 months follow-up after nail implant.

7.2 Secondary Objectives

The secondary objective of this study is to evaluate the safety profile of the long variant of the CHIMAERA™ used in adult patients according to the manufacturer IFU in routine clinical practice since nail application until 6 months after nail implant.

8. STUDY DESIGN

8.1 Research Type

The CHIMAERA study is designed as a retrospective, non-interventional, multicenter, PMCF study intended to evaluate both clinical benefit and safety profile of CHIMAERA™ device in adult patients according to the manufacturer IFU in routine clinical practice.

The study has been designed to retrospectively analyze the patient's medical records of patients who underwent a surgical implantation of CHIMAERA™ part of the site routine clinical practice. Data collection will be carried out during the study observation period, from the surgery until the last follow-up visit within 12-months after nail implant. Information will be collected from the different evaluations made by the subject in accordance with routine clinical practice, including the day of surgery, the hospital discharge, the bone consolidation assessment (1st follow up visit), the second follow up visit (2nd follow up visit), the last follow-up visit (3rd follow up visit), and additional surgeries if it occurred within 12 months after nail implant. Surgeons belonging to the 2 study sites who will participate in the study must have full awareness of orthopedic fixation procedures and should be familiar with the devices, instruments and surgical procedure, including the application and removal. After reviewing the selection criteria and confirming patient eligibility, demographic, and clinical and safety information from the time of surgery until the last follow-up visit will be collected from medical records.

To ensure the observational nature of the study, study data (demographics, clinical performance and safety data) will be collected from data already recorded in the medical records according to routine clinical practice. No diagnostic or therapeutic intervention outside of routine clinical practice will be applied.

The use of primary data sources is justified since it can provide the information needed to answer the primary objective in a cost-effective manner and using already available data. Patients' medical records are expected to contain all the required information. Due to the pure

retrospective design of the study with exclusive use of primary data sources, no study visit will be required, but according to local legislation, it will be essential that before collecting any information from medical records, participants or their guardians are asked for informed consent (IC). Once the IC is signed and the patient's eligibility is confirmed, the investigator will initiate accurate and appropriate data collection.

Due to the retrospective nature of the study, the decision on the prescription of Intramedullary nailing technique with CHIMAERA™ was under the discretion of the physician and it was made prior to the inclusion of the patient in the study. All participant patients had already undergone surgery through the intramedullary nailing technique using CHIMAERA™ under clinical practice conditions.

Individual patient data will be collected as pseudonymized in an electronic database designed specifically for this study.

Data collection will be carried during 4Q 2023-1Q 2024.

8.2 Subjects and Sites Numbers

It is planned to include non-competitively a consecutively a maximum of 44 subjects meeting the inclusion and exclusion criteria (Considering an imprecision of 5%) in two investigational sites located both in Italy. Clinical data will be collected only on adult patients with a regular indication for the CHIMAERA™ as per IFU (no off-label use will be included) and who underwent surgery performed with the specific device.

8.3 Study duration

The study will start in 4Q 2023, but these times may be modified by the administrative processing periods for initiation of the study. The enrollment period will be for 3 months, and the study will last approximately 6 months from the start of recruitment until the report of results.

Start of data collection (Start of recruitment)	4Q 2023
End of data collection	1Q 2024
Database lock	1Q 2024
Statistical analysis	2Q 2024
Final report on operations and results	2Q 2024
Study duration	12 months

8.4 Measures to Minimize or Avoid Bias

The herein proposed study design presents some methodological limitations that deserve to be highlighted. First, this study was designed to collect available information derived from clinical practice, so some of the assessments might not be available for some participants or at certain evaluations. Therefore, a reporting bias could occur. This bias refers to errors introduced during the measurement of study variables, which may affect the study results and estimates. To minimize this risk of bias, unavailable data/assessments will be declared as unavailable and left as missing in the statistical analysis. However, it is expected that most of the data of interest in this study will be recorded in the medical records, as they are part of the usual clinical practice of these patients in Italy.

In addition, the possible occurrence of selection bias cannot be ruled out. However, to minimize their occurrence, the investigator will begin inclusion of patients in the study with the last patient meeting the inclusion/exclusion criteria. It will then continue with the inclusion of patients meeting the inclusion/exclusion criteria following a chronological order prospectively over time according to the list of subjects with a regular indication for CHIMAERA™ as per IFU.

On the other hand, the fact that it is a multicenter study that includes information in different ways could generate variability in data collection between study sites and countries. This variability is part of real clinical practice and is therefore an intrinsic limitation of this type of study.

Finally, like most observational studies, potential confounding bias should be considered. When an exposure of interest is strongly associated with another exposure that is also related to the outcome, confounding bias could exist. According to previous data obtained with the use of CHIMAERA™, in the present study it is expected that the results obtained from the primary endpoint regarding the clinical benefit will be in line with those obtained in previous studies in order to support the pre-market clinical evaluation of the CHIMAERA™ with Real World Evidence clinical data in a real-life surgical setting confirming his benefit/risk ratio.

8.5 Prematurely End of the Study (EOS)

The end of study is defined as all close out visits and database lock performed.

This study may be prematurely terminated by decision of the regulatory authorities or at the sponsor's discretion. This decision will be communicated in writing to the investigator.

The study sponsor has the right to replace a site at any time for poor recruitment, poor Clinical Investigation Plan adherence, inaccurate or incomplete data recording, noncompliance with the Guidelines for Good Pharmacoepidemiology Practice or any other pertinent local law or guideline.

Likewise, if the investigator decides to withdraw from the study, he/she must notify the sponsor immediately in writing.

9. SELECTION AND WITHDRAWAL OF SUBJECTS

9.1 Subject Inclusion Criteria

Patients eligible for inclusion in this study must meet all of the following criteria:

1. Patients who had a regular indication for surgical intervention with the long variant of CHIMAERA™ according to the manufacturer's IFU.
2. Patients equal or older than 18 years at the time of surgery.
3. Patients who underwent surgery performed with CHIMAERA™.
4. Patients with clinical data registered in her/his medical records sufficient to assess the safety and efficacy endpoints of the study.

10. TREATMENT OF SUBJECTS

10.1 Study Investigational Product(s)

The CHIMAERA™, is an internal fixation system intended for insertion into the medullary canal of a femur in individuals suffering from stable and unstable pectrochanteric, intertrochanteric and subtrochanteric fractures of the femur. Its unique and distinguishing feature is the revolutionary locking mechanism of the lag screw that efficiently secures it to the nail without the need for a set screw. This implant is composed by 2 nails of sterile titanium (1 short and 1 long) with diameters of 10 and 11 mm for distal and 15.5 mm for proximal, different lengths comprises from 280 to 450 mm and with a 125° or 130° CCD angle in order to assure compatibility with patient anatomy. The device is also composed by end caps, lag screws,

threaded locking screw and an supplementary lag screw made all of stainless steel, aluminum alloy, carbon fiber, composite and plastic (85).

It is a class I, IIa and IIb non-absorbable and long-term surgically invasive implantable device manufactured by Orthofix S.r.l that has been CE marketed since 2018. CHIMAERA™ is intended for insertion into the medullary canal of a femur for the alignment, stabilization and fixation of various types of fractures or deformities. It is indicated for treatment of stable and unstable pectrochanteric, intertrochanteric and subtrochanteric fractures of the femur alone or when these fractures occur in combination with shaft fractures extending distally to a point approximately 10cm proximal to the intercondylar notch. These include traumatic fractures, re-fractures, non-union, reconstruction, malunion, malalignment, pathological fractures, and impending pathological fractures (86).

The Use of the CHIMAERA™ is contraindicated for patients with general medical conditions not suitable for surgery, active or suspected latent infections in the fracture area and suspected or documented metal allergy or intolerance (86).

Through the use experience of CHIMAERA™, the following adverse effects are registered: delayed union or non-union of the fracture site; breakage of the device when subjected to the increased loading with delayed union and/or non-unions, conditions attributable to non union (osteoporosis, osteomalacia, diabetes, inhibited revascularization and poor bone formation causing loosening, bending, cracking, fracture of the device or premature loss of rigid fixation with the bone); mal-union of the bone and/or bending, cracking or even breakage of the device due to improper alignment; increased fibrous tissue response around the fracture site due to unstable comminuted fractures; early or late infection, both deep or superficial; thromboembolic events; fat embolism; avascular necrosis; shortening of the effected bone/fracture site; subclinical nerve damage due to the surgical trauma; material sensitivity reactions in patients following surgical implantation. Further details are provided in the IFU (17.2) (86).

CHIMAERA™ nail has not been evaluated for safety and compatibility in the Magnetic Resonance (MR) environment. It has not been tested for heating, migration, or image artifact in the MR environment. The safety of CHIMAERA™ nail in the MR environment is unknown. Scanning a patient who has this device may result in patient injury (85).

10.1.1 Intended purpose / Intended Use of the Investigational Device

In this study, the intended use of CHIMAERA™ is focused on adult patients that have been treated for of stable and unstable pectrochanteric, intertrochanteric and subtrochanteric fractures of the femur alone or when these fractures occur in combination with shaft fractures extending distally to a point approximately 10cm proximal to the intercondylar notch.

The target population is broad, with no restrictions apart from those stated in the inclusion/exclusion criteria. Details on the routine intended purpose/use of CHIMAERA™ are provided in the IFU (17.2) (86).

10.2 Application of the device

The application of CHIMAERA™ has been performed according to routine clinical practice, without restrictions derived from patient participation in the study.

How to proceed in a particular surgery depends on the surgical requirements, where nails should be inserted depending on the bone to be treated, fracture severity, product knowledge, the patient's condition and surgeon's experience. Details on the routine application of CHIMERA™ are provided in the IFU (17.2) (86).

For further information on CHIMAERA™ nail, please refer to the Operative Technique published in: <https://abscdn.orthofix.it/resources/HF-1501-OPT-E0.pdf> (85).

11. STUDY PROCEDURES

11.1 Description of Procedures

To ensure the observational nature of the study, all data will be collected if they are available in the patient's medical record. The degree of detail and completeness of data collected will therefore be dependent on the availability of data in medical charts and the routine clinical practice of the two participating sites. There are no Clinical Investigation Plan visits imposed, or procedures outside the usual clinical practice to guarantee that the study does not modify in any way the healthcare professional prescription habits or his/her healthcare practice. Unavailable data/assessments will be stated in the electronic Case Report Form (eCRF) as not available.

At the screening phase, only to patients who meet all inclusion and exclusion criteria the investigator will ask if he/she is willing to participate to the study and provide the Information sheet to the patient (and to the legal representative/guardian if applicable). Together with providing the Information sheet, the investigator (or an authorized designee) must also orally inform the patient (and the legal representative/guardian if applicable) about the objectives, procedures and duration of the study as well as the foreseeable risks and potential benefits deriving from participation in the same.

According to local legislation, it will be essential that before collecting any information from patient's medical records, participants or their guardians are asked for informed consent (IC). Once the IC is signed and the patient's eligibility is confirmed, the investigator will initiate accurate and appropriate data collection.

Upon confirmation that the patient meets all the selection criteria, the physician participating in the study will proceed to extract the available study data (previously registered) in the patient's medical records.

The clinical benefit and the safety profile will be assessed since surgery within 12 months and until 6 months follow-up respectively after nail implant through the information collected from the medical records of the two participating sites.

All data, recorded in an electronic CRF, will be analyzed at the end of the study.

11.2 Study data collection

At the time of data collection, once the eligibility of patients has been confirmed, patients will be considered included and they will be assigned a permanent identification number so that the information managed does not contain personal data.

The procedures and data required are the following:

- Review of selection criteria and obtaining informed consent
- Sociodemographic characteristics (Age at surgery, gender, ethnicity)
- Anthropometric data (weight, height, Body Mass Index (BMI))
- Anamnesis data (worker, smoker, alcohol user)
- Relevant medical history (specifically related to other fractures that have occurred previously)
- Comorbidities (other acquired or congenital deformities)
- Clinical diagnosis: date of trauma, type and classification of fracture, cause of fracture, non-union, pathological fracture, results of RX diagnosis performed if available.
- Related surgery data:
 - Date of surgery
 - Femur-treated
 - Operation time
 - Antibiotic prophylaxis
 - CHIMAERA™ specification device (use of CHIMAERA™, nail composition, CCD angle, distal diameter, height and length of nail, type of lag screw, use of additional lag screw, distally lock of the nail, other synthetic media applied and device code)
 - Post-operative ADEs/SADEs and MDDs related to CHIMAERA™ (including blood loss)
 - Intraoperative fluoroscopy and time of fluoroscopy
 - Tip Apex Distance (TAD) calculation
 - Need of blood transfusion and number of blood bags used
 - Intraoperative measures (for corrections) (number of osteotomies, rotational correction, varus/valgus correction, shortening)
- Hospital stay data (date of hospital admission, date of hospital discharges, stay duration, presence of pain at the site of nail insertion)
- 1st follow up visit (Bone consolidation assessment data): date of assessment, fluoroscopy or RX performed, TAD calculation, bone consolidation/union (yes/no) by both observers, presence of pain at the site of nail insertion.
- 2nd follow up visit (): date of visit, presence of pain at the site of nail insertion.

- Last Follow-up visit (date of assessment, fluoroscopy or RX performed, TAD calculation, bone consolidation/union (yes/no) by both observers if not achieved in the last visit, presence of pain at the site of nail insertion).
- Reoperations (date, duration, post-operative x-ray, need of blood transfusion, intraoperative fluoroscopy and measures and main reasons of reoperation) performed within the 12 months after nail implant.
- ADEs/SADEs reported since the day of surgery until the last follow-up visit.
- MDDs reported since the day of surgery until the last follow-up visit.
- Concomitant medication prescribed since surgery until the last follow-up visit.

12. ADVERSE EVENTS AND SERIOUS ADVERSE EVENTS

As this is a study based on primary use of data, safety monitoring and safety reporting, where there is a safety relevant result, will be provided on an aggregate level only, no reporting on an individual case level.

In studies based on primary use of data with a safety relevant result, reports of adverse events/adverse reactions will be summarized in the study report, i.e. the overall association between an exposure and an outcome will be presented. All Adverse Events (AEs) and device deficiencies will be collected and reported to the sponsor.

The following definitions are provided in accordance with MDR (EU) 2017/745 of the European Parliament and of the Council on medical devices (28) and its guidelines as MDCG 2020-10/1 (29) and ISO/DIS 14155:2020 (27).

12.1 Definitions

Adverse event (AE)

Any untoward medical occurrence, unintended disease or injury, or untoward clinical signs, symptom or medical condition (including abnormal laboratory findings) in patients, users or other persons, whether or not related to the investigational medical device (MDR Article 2(57)).

- a. This definition includes events that are anticipated as well as unanticipated events.
- b. This definition includes events occurring in the context of a clinical investigation related to the investigational device, the comparator or the procedures involved (MDCG 2020-10/1) (29).

Adverse Device Effect (ADE)

Any AE related to the use of an investigational medical device, including adverse events resulting from insufficient or inadequate IFU, deployment, implantation, installation, or operation, or any malfunction of the investigational medical device and any event resulting from use error or from intentional misuse of the investigational medical device. (ISO 14155:2020).

Serious Adverse Event (SAE)

AE that led or could have led to any of the following:

- a) Death,
- b) Serious deterioration in the health of the patient, users or other persons as defined by one or more of the following:
 - 1) a life-threatening illness or injury, or
 - 2) a permanent impairment of a body structure or a body function including chronic diseases, or
 - 3) in-patient or prolonged hospitalization, or
 - 4) medical or surgical intervention to prevent life-threatening illness or injury or permanent impairment to a body structure or a body function,
- c) Fetal distress, fetal death or a congenital abnormality or birth defect including physical or mental impairment (MDR Article 2(58))

Serious Adverse Device Effect (SADE)

ADE that has resulted in any of the consequences characteristic of a serious adverse event (ISO 14155:2020).

Medical Device Deficiency (MDD)

Inadequacy of a medical device with respect to its identity, quality, durability, reliability, usability, safety or performance. Device deficiencies include malfunctions, use errors, and inadequacy in the information supplied by the manufacturer including labelling (Article 2(59) of the MDR).

Unanticipated serious adverse device effect (USADE)

Any SADE which by its nature, incidence, severity or outcome has not been identified in the current version of the risk analysis report and is therefore not included in the IFU (ISO 14155:2020).

Anticipated serious adverse device effect (ASADE)

SADE which by its nature, incidence, severity or outcome has been identified in the risk analysis report and is therefore included in the IFU (ISO 14155:2020).

12.2 Procedures for Reporting and Recording Adverse / Serious Adverse Events

Since this study is intended to collect safety information retrospectively related to the use of CHIMAERA™, the Investigators must record and document in detail all adverse events according to the designated eCRF page. All serious adverse events, whether or not deemed

investigational device related or expected, and all serious adverse device effects will be collected.

The following information on all AEs/SAEs will be recorded on the Adverse Event Form in the CRDe:

- Description of the event.
- Start and end dates.
- Maximum intensity reached.
- Causal relationship to the study device/procedure (unrelated, unlikely, possible, probable, causal relationship).
- Severity (yes/no).
- Actions taken in relation to the study product/device.
- Status of the event (resolved, resolved with sequelae, fatal, improved, ongoing, worsening, unknown).
- If serious: Severity criteria (death, life-threatening, hospitalisation or prolonged hospitalisation, permanent or significant disability, congenital anomaly, medically significant, transmission of infectious agent, serious injury or death due to device malfunction, medical or surgical intervention to prevent permanent damage).

As this is a non-interventional post-authorisation study, reporting of both serious and non-serious adverse events will not be required. In addition, as this is a retrospective study, adverse events are considered to have been previously reported. However, All SAEs will be reported to the sponsor through the SAE form and recorded into the safety database of the sponsor at the end of the study.

12.3 Assessment of causality

The relationship between the use of the medical device (including the medical-surgical procedure) and the occurrence of each adverse event shall be assessed and categorized.

During causality assessment activity, clinical judgement shall be used and the relevant documents, such as the Investigator's Brochure, the Clinical Investigation Plan or the Risk Analysis Report shall be consulted, as all the foreseeable serious adverse events and the potential risks are listed and assessed there. The presence of confounding factors, such as concomitant medication/treatment, the natural history of the underlying disease, other concurrent illness or risk factors shall also be considered.

The above considerations apply also to the serious adverse events occurring in the comparison group.

For the purpose of harmonizing reports, each SAE will be classified according to four different levels of causality:

1. Not related.
2. Possible.
3. Probable.
4. Causal relationship,

The sponsor and the investigators will use the following definitions to assess the relationship of the serious adverse event to the investigational device, the comparator or the investigation procedure.

1. Not related: Relationship to the device, comparator or procedures can be excluded when:

- the event has no temporal relationship with the use of the investigational device, or the procedures related to application of the investigational device.
- the serious adverse event does not follow a known response pattern to the medical device (if the response pattern is previously known) and is biologically implausible.
- the discontinuation of medical device application or the reduction of the level of activation/exposure - when clinically feasible - and reintroduction of its use (or increase of the level of activation/exposure), do not impact on the serious adverse event.
- the event involves a body-site or an organ that cannot be affected by the device or procedure.
- the serious adverse event can be attributed to another cause (e.g. an underlying or concurrent illness/clinical condition, an effect of another device, drug, treatment or other risk factors).
- the event does not depend on a false result given by the investigational device used for diagnosis, when applicable.

In order to establish the non-relatedness, not all the criteria listed above might be met at the same time, depending on the type of device/procedures and the serious adverse event.

2. Possible: The relationship with the use of the investigational device or comparator, or the relationship with procedures, is weak but cannot be ruled out completely. Alternative causes are also possible (e.g., an underlying or concurrent illness/ clinical condition or/and an effect of another device, drug or treatment). Cases where relatedness cannot be assessed, or no information has been obtained should also be classified as possible.

3. Probable: The relationship with the use of the investigational device or comparator, or the relationship with procedures, seems relevant and/or the event cannot be reasonably explained by another cause.

4. Causal relationship: the serious adverse event is associated with the investigational device, comparator or with procedures beyond reasonable doubt when:

- the event is a known side effect of the product category the device belongs to or of similar

devices and procedures.

- the event has a temporal relationship with investigational device use/application or procedures.
- the event involves a body-site or organ that:
 - the investigational device or procedures are applied to.
 - the investigational device or procedures have an effect on.
- the serious adverse event follows a known response pattern to the medical device (if the response pattern is previously known).
- the discontinuation of medical device application (or reduction of the level of activation/exposure) and reintroduction of its use (or increase of the level of activation/exposure), impact on the serious adverse event (when clinically feasible).
- other possible causes (e.g. an underlying or concurrent illness/ clinical condition or/and an effect of another device, drug or treatment) have been adequately ruled out.
- harm to the subject is due to error in use.
- the event depends on a false result given by the investigational device used for diagnosis, when applicable.

In order to establish the relatedness, not all the criteria listed above might be met at the same time, depending on the type of device/procedures and the serious adverse event.

The sponsor and the investigators will distinguish between the serious adverse events related to the investigational device and those related to the procedures (any procedure specific to the clinical investigation). An adverse event can be related both to procedures and the investigational device. Complications caused by concomitant treatments not imposed by the clinical investigation plan are considered not related. Similarly, several routine diagnostic or patient management procedures are applied to patients regardless of the clinical investigation plan. If routine procedures are not imposed by the clinical investigation plan, complications caused by them are also considered not related.

In some particular cases the event may not be adequately assessed because information is insufficient or contradictory and/or the data cannot be verified or supplemented. The sponsor and the Investigators will make the maximum effort to define and categorize the event and avoid these situations. Where an investigator assessment is not available and/or the sponsor remains uncertain about classifying the serious adverse event, the sponsor should not exclude the relatedness; the event should be classified as “possible” and the reporting as not delayed. Particular attention shall be given to the causality evaluation of unanticipated serious adverse events. The occurrence of unanticipated events related could suggest that the clinical investigation places subjects at increased risk of harm than was to be expected beforehand.

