24.2 ADVERSE EVENTS

The categorical variables to be described are, N and (%) and Clopper-Pearson confidence intervals will be shown at 95.0% as well:

- Patients with at least one adverse event
- Patients with at least one serious adverse event
- Patients with at least one related adverse event (considering related as Possible, Probable and Casual relationship)
- Patients with at least one adverse event which require additional surgery

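### Protocol section 12.3 is inconsistent on whether complications of the CHIMAERA implantation count as related, so the same surgical complication could be coded either way

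*Protocol*

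**What the plan says.** Several parts of the protocol place the operation inside the causality assessment:

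- Section 12.3 begins by requiring assessment of "The relationship between the use of the medical device (including the medical-surgical procedure) and the occurrence of each adverse event". Its first criterion for a not-related grade also refers to procedures connected with applying the device.
- Section 12.1 defines an adverse device effect as "including adverse events resulting from insufficient or inadequate IFU, deployment, implantation, installation, or operation".
- Section 10.1 lists adverse effects registered with CHIMAERA. They include infection, thromboembolic events, fat embolism and "subclinical nerve damage due to the surgical trauma".
- Section 11.2 collects blood loss among the post-operative device-related events, and section 12.2 records causality against the study device or procedure.

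The closing part of section 12.3 reads differently. Sponsor and investigators are to separate device-related serious events from "those related to the procedures (any procedure specific to the clinical investigation"). It then observes that "several routine diagnostic or patient management procedures are applied to patients regardless of the clinical investigation plan", and concludes: "If routine procedures are not imposed by the clinical investigation plan, complications caused by them are also considered not related".

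On design, section 8.1 states: "No diagnostic or therapeutic intervention outside of routine clinical practice will be applied". It adds that the choice of nailing was made before inclusion. Section 10.2 says the device was applied in routine practice.

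On outcomes, the first branch of the safety endpoint in section 13.1.2.2 is reoperation caused by an adverse effect potentially or certainly related to CHIMAERA. The second branch is a device deficiency that affected the patient. SAP section 24.2 reports "Patients with at least one related adverse event (considering related as Possible, Probable and Casual relationship").

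**The concern.** The closing wording of section 12.3 suits an interventional investigation, where procedures added by the plan can be told apart from background care. Here the plan adds no procedure, so the set of procedures specific to the investigation is empty. The nailing is routine and not imposed by the plan, and that is the condition the rule sets for a not-related grade.

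An investigator who starts from the opening of the section would grade a surgical complication for relatedness. One who applies the closing rule literally could code it not related. Both could cite section 12.3, which gives no order of precedence. The second choice removes the event from any output that depends on relatedness, so the bias has one direction: towards a more favourable safety profile, in a study intended to confirm benefit/risk and support the CE mark (section 6.2).

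**Working it through.** The point is textual, and the plan gives no figure to reproduce. The check has three steps.

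**1. Do the conditions of the closing rule fit the nailing?**

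- Is the procedure routine? Yes (section 10.2).
- Is it imposed by the plan? No (section 8.1).
- Is it within procedures specific to the investigation? No, because there are none.
- Is it exempted anywhere in the closing text? No. The preceding sentence speaks of diagnostic and patient-management procedures, which points to a narrower intent, but the rule itself refers to routine procedures without limit.

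The literal reading is available but not compelled. The opening of section 12.3, the ADE definition and the list in section 10.1 all point the other way. Even if the routine-procedure rule is confined to diagnostic and management procedures, the restriction to procedures specific to the investigation still leaves no procedure-related class for a complication of the operation.

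**2. Which outputs depend on the causality grade?**

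| Output | Depends on relatedness? |
|---|---|
| SAP 24.2: patients with at least one related adverse event | Yes |
| Protocol 13.1.2.2 and 13.1.3.2: reoperation, actual or hypothetical, due to an ADE/SADE | Yes |
| Same endpoint: reoperation due to a device deficiency | No |
| SAP 24.1.1: patients with additional surgery because of an adverse event or a device deficiency | No |
| SAP 24.2: patients with an adverse event requiring additional surgery | No |

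A patient leaves a related count only if the recoded event was the only qualifying one. A patient who also has another related event stays in both exposed counts. A qualifying device deficiency keeps a patient in the combined reoperation endpoint.

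**3. Scale**

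Inputs: n = 44, the planned maximum (protocol section 13.2); literature reoperation rate due to ADEs/SADEs averaging 5.9%, range 0.0% to 27.5% (section 6.1); Clopper-Pearson 95% intervals (SAP section 14).

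- Step per recoded patient: 1/44 = 2.3 percentage points. A safety population below 44 would make the step larger.
- Expected patients with reoperation at the literature average: 44 × 0.059 = 2.6. Across the range: 44 × 0 = 0 to 44 × 0.275 = 12.1.
- Interval for x of n: the lower limit is the 2.5% quantile of Beta(x, n − x + 1) and the upper limit is the 97.5% quantile of Beta(x + 1, n − x).
- 3/44 = 6.8% (1.4% to 18.7%).
- 2/44 = 4.5% (0.6% to 15.5%).

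The last two lines show what one recoded patient would do if three had qualified. Both the three and the one are assumptions.

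**The case against.** The strongest reply is that the closing rule should be read with the sentence before it. That sentence concerns diagnostic and patient-management procedures and is paired with concomitant treatments. Neither describes implanting the device under study. The reply can add that the grading criteria name procedures connected with applying the device, that an event may be related to both procedure and device, and that unassessable or uncertain cases default to possible, which the SAP counts as related.

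Most of this stands. It shows that the probable intent is to keep implantation complications within relatedness. It does not settle the text. The default to possible helps only where an assessment is missing or uncertain, and an investigator following a stated rule is neither. The ADE definition names inadequate implantation, so an infection or embolism after competent surgery is not clearly caught by those words. The causal criteria rely on the term procedures, which the closing text narrows.

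The reply is also right about reach. The SAP's additional-surgery counts carry no relatedness filter, events graded not related are still tabulated (SAP section 24.2.2), and all events are listed. The unfiltered counts are not the protocol's endpoint, however. Its ADE/SADE branch needs the causality grade.

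**Conclusion.** Section 12.3 conflicts with itself and with sections 12.1 and 10.1 on whether implantation complications count as related. The conflict can bias downward the SAP count of patients with a related adverse event and the ADE/SADE branch of the protocol's safety endpoint, by 2.3 points per patient recoded out of 44. This assumes that at least one investigator applies the closing rule literally to an event that was the patient's only qualifying one. The documents give no basis for estimating how often that would happen.

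A reader might infer more, and the documents do not support it:

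- **That the nailing plainly falls under the rule, so surgical complications are excluded.** The surrounding text points mostly the other way. The defect is ambiguity.
- **That the reoperation rate could fall to zero.** This needs every reoperation to be purely procedural and recoded, with none due to a device deficiency or an implant-related effect.
- **That the result would not be comparable with the 5.9% literature average.** The documents do not say how the cited studies attributed surgical complications, and the plan sets no test or threshold against that figure.
- **That events have already been miscoded.** Nothing in either document shows this.

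**What to change.** Reconcile the closing part of section 12.3 with its opening and with section 12.1:

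1. Replace the restriction to procedures specific to the investigation with wording such as: *for causality assessment, procedures include the CHIMAERA implantation and any later operation on it, although these are routine care.*
2. State that the routine-procedure rule covers only diagnostic or patient-management procedures unconnected with the implant.
3. Repeat both points in the eCRF completion note before causality is coded.

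The cost is a sentence or two of protocol wording and a short note to two sites. No analysis changes. The related-event rate may come out slightly less favourable.
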